3.2. Schedule of Events

Schedule of events can be found in Section 1.3 Table 1 of the protocol.

3.3. Changes to Analysis from Protocol

Serious adverse events (SAEs), TEAEs leading to death and TEAEs leading to discontinuation from study will be listed.

[REDACTED]

4. PLANNED ANALYSES

The following analyses will be performed for this study:

- Analysis for Safety Review Committee (SRC)
- Final Analysis

4.1. Safety Review Committee

The SRC will review safety results and preliminary plasma PK data. For additional details pertaining to these data reviews and analyses, refer to the SRC Charter. Preliminary PK parameters will be calculated by using available quality-controlled CS-1103 concentrations and scheduled sampling times to support dose-escalation decisions, as applicable.

4.2. Final Analysis

All final, planned analyses identified in this SAP will be performed by IQVIA Biostatistics following Sponsor Authorization of this Statistical Analysis Plan, Database Lock, and Unblinding of Treatment.

5. ANALYSIS SETS

5.1. All Participants Screened Set

[figure not shown]
The all participants screened set will contain all participants who provide informed consent for this study.

5.2. Safety Analysis Set

The safety analysis set will contain all participants who receive study treatment (CS-1103 or placebo). Participants will be classified according to treatment received.

5.3. Pharmacokinetic Analysis Set

The pharmacokinetic analysis set will consist of all participants who receive active study treatment (CS-1103) and

have at least 1 measured plasma or urine concentration at a scheduled PK time after start of dosing for at least 1 PK analyte without protocol deviations or events with potential to affect the pharmacokinetic concentrations. Participants in this population will be used for all PK analyses.

6. GENERAL CONSIDERATIONS

Derivation of the PK parameters will be the responsibility of the clinical pharmacokineticist at IQVIA. The PK and safety summaries, data listings and figures as well as the statistical analysis of the PK variables will be the responsibility of the study biostatistician at IQVIA.

6.1. Summary Statistics

For qualitative variables, the population size (N for sample size and n for available data) and the percentage (of available data) for each class of the variable will be presented. Quantitative safety variables will be summarized using descriptive statistics, including N, n, mean, standard deviation (SD), coefficient of variation (CV%) as appropriate, median, minimum, and maximum values. Geometric mean and geometric CV% will be included for PK parameters, where applicable. CV will not be presented for change from baseline results.

[figure not shown]
6.2. Treatment Summarization

In general, data will be presented for each active treatment group, with placebo participants from all dose groups combined into a single, overall placebo group. Data for all study participants combined or all active-treated subjects will also be presented when appropriate.

6.3. Precision

Safety variables (ie, clinical laboratory values, vital signs, and ECG intervals), including derivations thereof, will be reported to the same precision as the source data.

All PK concentrations will be reported and analyzed with the same precision as the source data provided by the bioanalytical laboratory regardless of how many significant figures or decimals the data carry. Derived PK parameters will be rounded for reporting purposes in by-participant listings. The rounded derived PK data will be considered the source data for the calculation of descriptive statistics and the statistical analysis. For most derived PK

parameters, 3 significant digits will be used as the standard rounding procedure, with the following exceptions:

- Parameters directly derived from source data (eg, Cmax) will be reported and analyzed with the same precision as the source data.
- Parameters derived from actual elapsed sample collection times (eg, tmax) will be reported with the same precision as the actual elapsed sampling time value of the source data.

For the reporting of descriptive statistics, the mean (arithmetic or geometric), standard deviation, standard error and confidence intervals will be presented to one digit more precision than the source data. The minimum, median, and maximum will be presented to the same precision as the source data. Coefficient of variation will always be reported to 1 decimal place.

6.4. Reference Start Date and Study Day

Study Day will be calculated from the reference start date and will be used to show start/stop day of assessments and events. It will appear in every listing where an assessment date or event date appears.

[figure not shown]
Reference start date is defined as the day of study drug administration (Day 1 is the day of study drug administration).

- If the date of the event is on or after the reference date, then:
- Study Day = (date of event – reference date) + 1.
 - If the date of the event is prior to the reference date, then:
- Study Day = (date of event – reference date).

In the situation where the event date is partial or missing, Study Day, and any corresponding durations will appear partial or missing in the listings.

6.5. Baseline

Unless otherwise specified, baseline is defined as the last non-missing measurement taken prior to reference start date (including unscheduled assessments). In the case where the last non-missing measurement and the reference start date coincide, that measurement will be considered pre-baseline if the assessment is planned per protocol to take place prior to study treatment administration, otherwise, that measurement will be considered post-baseline. Adverse Events (AEs) and medications commencing on the reference start date will be considered post-baseline

unless otherwise indicated based on available start date/time combination or collected eCRF information that identifies the individual event/medication as starting prior to study treatment administration.

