6.6. Retests, Unscheduled Visits and Early Termination Data

Unscheduled measurements will not be included in post-baseline summary statistics but will contribute to the assessment of clinical outliers where applicable. Early termination results will be recorded as such and included with the end of study summaries.

In the case of a retest of a scheduled assessment, the earliest available measurement for that scheduled time (i.e., the original assessment) will be used for summaries unless flagged as invalid.

Listings will include all scheduled, unscheduled, retest, and early discontinuation data.

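### SAP 6.5 sorts Day 1 measurements by planned rather than actual timing, so an unscheduled pre-infusion value is classed as post-baseline and the status of the scheduled predose value is unclear

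*SAP*

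**What the plan says.** SAP 6.4: "Reference start date is defined as the day of study drug administration". It is a date and carries no time.

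SAP 6.5, general rule: baseline is the "last non-missing measurement taken prior to reference start date (including unscheduled assessments").

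SAP 6.5, when the last value falls on the dosing day itself: "that measurement will be considered pre-baseline if the assessment is planned per protocol to take place", and the sentence continues "prior to study treatment administration, otherwise, that measurement will be considered post-baseline".

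SAP 6.5, next sentence: adverse events and medications starting on the dosing day are also post-baseline by default, but "unless otherwise indicated based on available start date/time combination or collected eCRF information" shows that they began before dosing. Measurements have no such exception.

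SAP 6.6: "Unscheduled measurements will not be included in post-baseline summary statistics but will contribute to the assessment of clinical outliers where applicable". A separate paragraph says that when a scheduled assessment is retested, the original value is used for summaries unless it is flagged as invalid.

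SAP 16.4 tabulates participants with clinically noteworthy ECG values postdose. SAP 16.4.1 gives numeric criteria for QTcF only, starting at 450 msec for absolute values and at an increase above 30 msec for change from baseline.

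**The concern.** ECGs and vital signs are among the primary safety endpoints. In a first-in-human trial with six active participants per dose level, each participant weighs heavily in a category count. A measurement repeated before dosing is often repeated because the first one looked abnormal. If its label depends on the schedule and not on the clock, a value obtained with no drug on board can be labelled as following treatment. The participant also loses what may be the best baseline value.

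There is a second, separate doubt. The SAP calls the scheduled Day 1 predose value *pre-baseline* and never defines that word. It does not say that this value is the baseline.

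**Working it through.** The plan gives no figure to reproduce. The check is to read SAP 6.4, 6.5, 6.6 and 16.4 together and trace the possible Day 1 cases.

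| Day 1 measurement | Actually taken | Class under SAP 6.5 as written | Class by clock time |
|---|---|---|---|
| Planned predose | before infusion | *pre-baseline* (undefined) | candidate baseline |
| Planned predose, taken late | after infusion start | *pre-baseline* | post-baseline |
| Unscheduled | before infusion | post-baseline | candidate baseline |
| Planned postdose or unscheduled | after infusion start | post-baseline | post-baseline |

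The second and third rows are misclassified, and the first is unclear.

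**Unscheduled pre-infusion ECG**
1. Its date equals the reference start date, so the clause that accepts unscheduled values (strictly before that date) does not reach it.
2. It was not planned as a predose assessment, so it is post-baseline.
3. As an unscheduled value it stays out of post-baseline summary statistics but goes into the outlier assessment (SAP 6.6).
4. It can then add to the QTcF count in SAP 16.4, unless the programmer reads *postdose* by the clock.

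**Can this arise?** Protocol Table 1 allows repeat vital signs when needed. Exclusion criterion 11 applies above 450 msec in men and above 470 msec in women, so a woman with QTcF between 450 and 470 msec is eligible and already lies in the lowest noteworthy band without any drug.

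**Weight of one participant** (full cohorts: 5 cohorts of 6 active and 2 placebo)
- One dose level: 1/6 = 16.7%.
- Pooled placebo: 5 × 2 = 10, so 1/10 = 10%.
- All active: 5 × 6 = 30, so 1/30 = 3.3%.

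These changes occur only if the participant has no genuine post-dose value in the same or a higher category.

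**Scheduled predose value, read literally.** If baseline must precede the calendar day of dosing, the ECG and vital signs taken within 60 minutes of the infusion are not baseline, and baseline falls back to Day -1 or earlier. Under Protocol Table 1, footnote a, a whole cohort may check in the day before sentinel dosing. The non-sentinel participants need not repeat the admission evaluations and have only vital signs and an event and medication review on the day before their own dose. Their last ECG before the dosing day could then be two days old, against one day for the sentinels.

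**Is a time-based rule feasible?** Protocol 6.4 records the start and end times of the infusion, and Protocol 8.2.3.1 requires the date and time on each ECG tracing. The documents do not say as explicitly that each vital-sign reading is timed, so the rule needs a fallback.

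**The case against.** Several counter-arguments have force.

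- **Retest reading.** A reader might infer that every Day 1 predose repeat is misclassified on any reading. The documents do not support that. A repeat of the planned predose ECG can be taken as a retest of a planned assessment under SAP 6.6. This narrows the point but does not settle it: SAP 6.5 takes the last value while SAP 6.6 takes the original for summaries, and neither says which one governs baseline.
- **The word postdose.** SAP 16.4 counts postdose values. Applied by clock time, that keeps a pre-infusion ECG out, so the miscount is possible and not certain.
- **Reach.** A reader might infer that every change-from-baseline summary is affected. It is not. Unscheduled values are excluded from post-baseline summaries. Hematology, chemistry and coagulation have no Day 1 predose draw. Vital signs have no outlier table, so for them the effect is limited to the choice of baseline. Holter and concentration-QT analyses are in a separate plan.
- **Meaning of pre-baseline.** Its natural sense is the opposite of post-baseline, and singling out planned predose values would be pointless if they were then discarded. The fallback to Day -1 is a literal reading and probably not the intention.
- **Frequency.** The repeat-ECG footnote in Protocol Table 1 concerns Day -1, which SAP 6.5 handles correctly, and the QTcF eligibility limits make a pre-infusion value above 450 msec uncommon.

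What remains is that correct output depends on a programmer interpreting or departing from the text. The same section already uses actual times for adverse events and medications.

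**Conclusion.** The point holds as a defect in a stated rule with limited reach. As written, SAP 6.5 misclassifies an unscheduled ECG or vital sign taken on Day 1 before the infusion, and treats a planned predose value taken after infusion start as pre-dose. It also leaves open whether the scheduled predose value is the baseline.

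The consequences are a possible wrong or lost baseline for the affected participant and, for ECG only, a possible false entry in the QTcF count. The size is one participant in 6, or one in 10 for pooled placebo. That illustration assumes full cohorts, a value not treated as a retest, *postdose* not applied by clock time, and no genuine post-dose value in the same or a higher category. The documents give no basis for estimating how often this would happen, or how far values would shift if baseline fell back to Day -1. No general distortion of the safety summaries is shown.

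**What to change.** Make these changes in the SAP before database lock and unblinding:

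1. **SAP 6.5.** Define baseline as the last non-missing valid value, scheduled or unscheduled, with a date and time before the start of infusion. Where replicates are taken, use the mean of the replicate set. Use the planned order only if the actual time is missing. Replace *pre-baseline* with *baseline*.
2. **SAP 6.6.** State which value governs baseline when a predose assessment is retested. Without this line, taking the last predose value in 6.5 would conflict with the rule in 6.6 that uses the original.
3. **SAP 16.4.** Count only values timed after the start of infusion in the noteworthy-value table.

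The cost is one rewritten rule in 6.5, a matching line in 6.6 and a clarification in 16.4. Trial conduct does not change. Infusion and ECG times are already recorded, and the planned-order fallback covers any reading without a time.

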6.6. Retests, Unscheduled Visits and Early Termination Data

Unscheduled measurements will not be included in post-baseline summary statistics but will contribute to the assessment of clinical outliers where applicable. Early termination results will be recorded as such and included with the end of study summaries.

In the case of a retest of a scheduled assessment, the earliest available measurement for that scheduled time (i.e., the original assessment) will be used for summaries unless flagged as invalid.

Listings will include all scheduled, unscheduled, retest, and early discontinuation data.

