- d. Includes over-the-counter medications, herbal medications/supplements, and other supplements.
- e. Clinical laboratory tests: hematology, clinical chemistry (including liver and renal function), coagulation, and urinalysis with microscopic examination to be performed at screening, on Admission/Day -1, Day 2 and EOS. In addition, urinalysis will be performed for each urine sample collected on Day 1. Protocol-required laboratory tests are detailed in [Section 10.2, Table 6](#).
- f. Triplicate 12-lead ECGs will be obtained following at least 5 minutes remaining in a supine position and collected before other simultaneously scheduled procedures, i.e., vital signs and blood collections. Single ECGs may be collected during the first 30 minutes post-EOI to allow completion of all simultaneously scheduled procedures (see [Table 2](#)).
- g. On Admission/Day -1, continuous Holter Monitoring will be performed for 4 hours. If needed, any repeat ECG needs to be performed in triplicate.
- h. On Day 1, continuous Holter Monitoring will commence approximately 1 hour prior to study treatment administration and continue through 24 hours postdose. The ECGs will be extracted from Holter to be time-matched with PK samples (see [Table 2](#)).
- i. Vital signs (Systolic, diastolic, and mean blood pressure, pulse rate, respiratory rate, oxygen saturation, and body temperature) will be measured following at least 5 minutes remaining in a supine position following ECG collection (see [Table 2](#) and [Section 8.2.2](#) for details). If needed, repeat vital signs may be performed.
- j. Complete physical examination at screening and at end of study. Brief physical examination on Admission/Day -1 at check-in, Day 2, and Day 3.
- k. On Day 1, the injection site will be evaluated prior to study treatment administration and again immediately after study treatment administration, in approximately (+15 minutes) hourly intervals for up to 6 hours postdose. Injection site assessment also occurs any time on Day 2, and any time prior to discharge from the CRU on Day 3. (see [Section 8.2.1.1](#) for details on the 4-point scale injection site assessment).

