16.3. Laboratory Evaluations

Laboratory results, with units provided by the local laboratory, will be included in the reporting of this study for hematology, clinical chemistry, coagulation, and urinalysis. A list of laboratory assessments to be included in the outputs is included in Table 5 of the protocol.

Protocol-specified clinical laboratory tests will be listed and summarized using descriptive statistics. Clinical laboratory data collected during study conduct, which were not required per protocol, such as for special testing to evaluate an AE, will be listed separately and not summarized.

Quantitative laboratory measurements reported as ‘< X’, i.e., below the lower limit of quantification, or ‘> X’, i.e., above the upper limit of quantification, will be converted to X for the purpose of quantitative summaries, but will be presented as recorded, i.e., as ‘< X’ or ‘> X’ in the listings.

The following summaries will be provided for laboratory data:

- Actual and change from baseline by visit and treatment (for quantitative measurements)
- Shift from baseline according to normal range criteria at each post-baseline visit
- Listing of laboratory results outside the normal range

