16.5. Vital Signs

The following Vital Signs measurements will be reported for this study: systolic and diastolic blood pressure, pulse rate, respiratory rate, heart rate, oxygen saturation, and body temperature.

The following summaries will be provided for vital signs data:

- Actual and change from baseline by visit and treatment

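### Unscheduled and worse-on-retest vital-sign and laboratory values reach listings, or the TEAE tables without the value, but no vital-sign or laboratory table

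*SAP*

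**What the plan says.** SAP 6.6 sets the general rule: "Unscheduled measurements will not be included in post-baseline summary statistics but will contribute to the assessment of clinical outliers where applicable". Where a planned reading is repeated, "the earliest available measurement for that scheduled time (i.e., the original assessment) will be used for summaries unless flagged as invalid". The same section ends: "Listings will include all scheduled, unscheduled, retest, and early discontinuation data".

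The outputs for each type of safety data are these:

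- **Vital signs (SAP 16.5).** One summary: "Actual and change from baseline by visit and treatment". No thresholds, outlier count or abnormal-value listing are planned.
- **Laboratory (SAP 16.3).** Actual and change values by visit; "Shift from baseline according to normal range criteria at each post-baseline visit"; and "Listing of laboratory results outside the normal range". Tests outside the protocol's list, "such as for special testing to evaluate an AE, will be listed separately and not summarized".
- **ECG (SAP 16.4 and 16.4.1).** A count of participants with noteworthy post-dose values, with criteria for QTcF only.

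The protocol expects readings off the schedule. Footnote i to the Schedule of Activities says "If needed, repeat vital signs may be performed". Section 8.0 allows unscheduled samples for safety or technical reasons. Section 8.2.5 asks for clinically significant abnormal results to be repeated until they settle.

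**The concern.** The rule in 6.6 takes unscheduled values out of the summaries and offers one other route into a summary, the assessment of outliers. That route leads somewhere only if such an assessment exists. It exists for QTcF and for nothing else, so for vital signs and laboratory results the exclusion has no counterpart.

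Both are primary safety endpoints (Protocol Section 3.0; SAP Section 2). Off-schedule readings are often taken because something looked wrong, so the values left out are not a random subset. A reader who works from the vital-sign and laboratory tables would not see how far such a value went, or that it occurred.

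**Working it through.** The point rests on tracing a value through the planned outputs. The plan states no figure of its own to reproduce, and the trial tests no hypothesis (Protocol 9.1).

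**Where an unscheduled post-dose value goes**

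| Data | Outlier criteria in SAP | Table for that data type | Listing |
|---|---|---|---|
| QTcF | Yes (16.4.1) | Noteworthy-value count (16.4) | Yes |
| Vital signs | None | None | General listing only |
| Protocol laboratory tests | None | None: summary and shift are by visit | General listing, and out-of-range listing if abnormal |

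**Retests.** The original value stays in the summary unless flagged invalid. If the original was abnormal and the repeat normal, the abnormal value is kept. If the repeat is worse, the worse value goes to listings only.

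**Laboratory gap in time.** Scheduled post-dose blood tests fall on Day 2 and at the end-of-study visit (Day 8 ±1), per footnote e of the Schedule of Activities. An abnormal unscheduled blood result on Day 1, or between those two visits, that is normal at both visits leaves every laboratory table unchanged.

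**Route through adverse events.** Clinically significant laboratory changes must be recorded as adverse events (Protocol 8.2.5), and clinically significant vital-sign findings meet the definition (Protocol 10.3.1). TEAEs are tabulated by SOC and PT (SAP 16.1.1). That table counts the event but does not carry the measurement. A value judged not clinically significant stays in listings.

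**Illustration.** Assume one of the six active participants in a cohort has a 40 mmHg fall in systolic pressure and the other five do not change. The 40 mmHg is an assumption; the first result below is the same for a fall of any size.

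- Seen on an unscheduled reading: change in the vital-sign table = 0.
- Seen on a scheduled reading: the mean change moves by 40/6 = 6.7 mmHg, and the minimum change shows −40, because SAP 6.1 includes minimum and maximum.
- In a per-participant largest-fall table that admits unscheduled values: 1/6 = 17% of the dose group, set beside pooled placebo.
- Pooled placebo: 2 per cohort × 5 cohorts = 10 if all cohorts run. The plan says up to 5, so the number runs from 2 to 10.

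**The case against.** The strongest reply is that little is lost. All values are listed, out-of-range laboratory results have their own listing, and with six active participants per cohort a reader can find an extreme by eye. A participant who is unwell has an adverse event, which is tabulated. The Safety Review Committee sees safety results before each escalation. Protocol 9.3.3 plans outlier tabulations for ECG only, so the SAP does not depart from it. All of this stands, and it keeps the point small. It does not put the values into a vital-sign or laboratory table.

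A reader might also infer more than the documents support:

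- *That extremes are averaged away.* They are not if scheduled: SAP 6.1 and Protocol 9.3.1 give minimum and maximum. Only off-schedule extremes are excluded.
- *That the tables could show no effect when one occurred.* The TEAE tables would count an event judged clinically significant. What they lack is its size, and abnormalities judged not significant.
- *That acute infusion effects are caught mainly off schedule.* Footnote j of the detailed schedule places blood pressure readings at 5 minutes into the infusion, at its end and 20 minutes after it.
- *That 6.6 excludes these readings because outlier tables will catch them.* It gives no reason, and it limits the outlier role to cases where one applies.

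Footnote i does not say why vital signs would be repeated, and Protocol 8.2.2 mentions repeats only for eligibility. It shows that repeats are allowed, not how often they will follow symptoms.

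**Conclusion.** The gap is real and narrow. As the SAP is written, unscheduled and worse-on-retest vital-sign and laboratory values are found only in listings, or as TEAEs without the value when judged clinically significant. They contribute nothing to the vital-sign and laboratory tables for these primary safety endpoints. It is clearest for vital signs, which have no threshold, count or abnormal-value listing. Laboratory results have a shift table and an out-of-range listing, but the shift is by visit.

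How much this matters depends on how many off-schedule readings are taken, which the documents cannot tell us. The conclusion also assumes that the output shells, which accompany the SAP but were not available for review, add no such table; the SAP text plans none. This is a cheap improvement to what the safety tables can show from data already collected. It is not a defect in safety oversight or in the recording of data.

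**What to change.** Settle both additions before unblinding.

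1. **SAP 16.5.** Add, by dose and pooled placebo, a summary of each participant's largest post-dose rise and largest post-dose fall from baseline for each vital sign, and lowest SpO2, using scheduled, unscheduled and retest values. Counts beyond the limits in exclusion criterion 9 (systolic >145 mmHg, diastolic >95 mmHg, heart rate <45 or >100 bpm) may be added as analysis flags only. Those limits have no low blood pressure or SpO2 bound, so they would miss the 40 mmHg fall in the illustration and cannot replace the rise-and-fall summary.
2. **SAP 16.3.** Add a shift from baseline to the worst post-dose value, once for the lowest and once for the highest, including unscheduled and retest results.
3. **SAP 6.6.** State that unscheduled and retest values enter these two tables and remain outside the by-visit summaries.

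The cost is two more tables, a sentence in 6.6 and a footnote. The footnote should say that symptomatic participants are measured more often, so their worst values are drawn from more readings and comparison with placebo needs that caution. No new data collection is needed, and the by-visit tables stay as planned.
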